3 HYPOTHESES, OBJECTIVES, AND ENDPOINTS

In healthy Chinese infants 48-63 days of age:

Objectives	Endpoints
Primary	

Objective: To demonstrate that the immunogenicity of IPV in the concomitant-use group is non-inferior to that in the staggered-use group. Hypothesis (H1): The seroconversion percentage at 1 month post dose 3 for each of poliovirus types 1, 2, and 3 in the concomitant-use group is non-inferior to those in the staggered-use group. The statistical criterion for non-inferiority requires that the lower bound of two-sided 95.0% confidence interval for the difference (concomitant-use group minus staggered-use group) in seroconversion percentages be greater than -10% for each poliovirus type.	
Neutralizing antibody seroconversion to each of poliovirus types 1, 2, and 3
Secondary	

Objective: To evaluate immune responses to IPV at 1 month post dose 3 in the concomitant-use and staggered-use groups as measured by geometric mean titers (GMTs) of neutralizing antibodies to poliovirus types 1, 2, and 3.Objective: To evaluate immune responses to IPV at 1 month post dose 3 in the concomitant-use and staggered-use groups as measured by the proportions of participants with neutralizing antibody titer $\geq 1:8$ and $\geq 1:64$ for each of poliovirus types 1, 2, and 3.	
Neutralizing antibody titer to each of poliovirus types 1, 2, and 3Neutralizing antibody responses to each of poliovirus types 1, 2, and 3

Objectives	Endpoints

 Objective: To evaluate the safety of concomitant administration of V260 and IPV based on the proportions of participants experiencing solicited injection-site adverse events (AEs), solicited systemic AEs, and serious AEs (SAEs). 	
 Solicited injection-site AEs (following vaccination of IPV) Solicited systemic AEs SAEs
Exploratory	

 Objective: To evaluate immune responses to V260 at 1 month post dose 3 in the concomitant-use and staggered-use groups using anti-rotavirus type-specific IgA based on GMTs and proportions of participants with ≥ 3-fold increase in titer post-vaccination from baseline. 	
 Anti-rotavirus type-specific IgA antibody responses to rotavirus serotypes G1, G2, G3, G4, and P1A[8]

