9.1 Statistical Analysis Plan Summary

Key elements of the statistical analysis plan are summarized below; the comprehensive plan is provided in Sections 9.2-9.12.

Study Design Overview	A Phase 3 Randomized, Open-Label, Clinical Trial to Study the Immunogenicity and Safety of Concomitant and Non-Concomitant Administration of V260 and Inactivated Poliomyelitis Vaccine (IPV) in Chinese Healthy Infants
Treatment Assignment	Participants will be randomly assigned in a 1:1 ratio to receive V260 and IPV in a concomitant-use or staggered-use schedule
Analysis Populations	Immunogenicity: Per-Protocol Immunogenicity (PPI) population Safety: All Participants as Treated (APaT) population

Primary Endpoint(s)	Immunogenicity: 
 Neutralizing antibody seroconversion percentages to each of poliovirus types 1, 2, and 3 at 1 month post dose 3 of IPV
Secondary Endpoints	Immunogenicity: 
 Neutralizing antibody geometric mean titers (GMTs) to each of poliovirus types 1, 2, and 3 at 1 month post dose 3 of IPV Proportions of participants with neutralizing antibody titer $\geq 1:8$ and $\geq 1:64$ at 1 month post dose 3 of IPV for each of poliovirus types 1, 2, and 3 Safety: 
 Proportions of participants with solicited injection-site AEs (erythema, swelling, induration, and pain at the injection-site of IPV) from Day 1 through Day 7 following any vaccination of IPV Proportions of participants with solicited systemic AEs (diarrhea and/or vomiting) from Day 1 through Day 7 following any vaccination of V260 and/or IPV Proportions of participants with SAEs from Day 1 through end of study
Statistical Methods for Key Immunogenicity Analyses	For the primary hypothesis, concomitant-use group will be considered non-inferior to staggered-use group if the lower bound of the two-sided 95% confidence interval (CI) for the difference in seroconversion percentage (concomitant-use group minus staggered-use group) is greater than -10% for each poliovirus type.
Statistical Methods for Key Safety Analyses	All safety data will be summarized as frequencies and percentages for the two vaccination groups.
Interim Analyses	No interim analysis is planned.
Multiplicity	Since success is required on all 3 poliovirus types for the primary hypothesis, no multiplicity adjustment will be made for the multiple tests.

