9.6 Statistical Methods

Statistical testing and inference for immunogenicity and safety analyses are described in Section 9.6.1 and Section 9.6.2, respectively. Unless otherwise stated, all statistical tests will be conducted at the $\alpha=0.025$ (1-sided) level.

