9.6.2 Statistical Methods for Safety Analyses

Safety and tolerability will be assessed by clinical review of all relevant parameters including AEs and post-vaccination temperature measurements.

An overall assessment of adverse events will be summarized for each group by dose period (dose period is defined in [Table 4](#)) and across all dose periods.

Table 4 Each Group by Dose Period

Dose Period	Concomitant-Use Group (Vaccine administered)	Staggered-Use Group (Vaccine administered)
1	Visit 2 (V260 + IPV)	Visit 1 (V260)
	Visit 3	Visit 2 (IPV)
2	Visit 4 (V260 + IPV)	Visit 3 (V260)
	Visit 5	Visit 4 (IPV)
3	Visit 6 (V260 + IPV)	Visit 5 (V260)
	Visit 7	Visit 6 (IPV)

Summary statistics, counts and percentage without confidence interval, will be provided by group. Proportions of participants with solicited injection-site AEs (following vaccination of IPV), solicited systemic AEs within 7 days following study vaccination will be given. Maximum axillary temperatures recorded on the VRC from Day 1 through Day 7 post-vaccination will be summarized. Table 5 shows the safety endpoints that will be summarized.

Table 5 Analysis Strategy for Safety Parameters

Safety Endpoints	Time Period	Descriptive Statistics
Solicited Injection-Site AEs	Days 1-7 post-vaccination of V260 and IPV in the concomitant-use group, and Days 1-7 post-vaccination of IPV in the staggered-use group, across all dose periods and by dose period	X
Solicited Systemic AEs	Days 1-7 post-vaccination of V260 and IPV in the concomitant-use group, and Days 1-7 post-vaccination of V260 plus Days 1-7 post-vaccination of IPV in the staggered-use group, across all dose periods and by dose period	X
Maximum Axillary Temperature	Days 1-7 post-vaccination of V260 and IPV in the concomitant-use group, and Days 1-7 post-vaccination of V260 plus Days 1-7 post-vaccination of IPV in the staggered-use group, across all dose periods and by dose period	X
Any Injection-Site AEs	Days 1-15 post-vaccination of V260 and IPV in the concomitant-use group, and Days 1-15 post-vaccination of IPV in the staggered-use group, across all dose periods and by dose period	X
Any Systemic AEs	Days 1-30 post-vaccination of V260 and IPV in the concomitant-use group, and Days 1-15 post-vaccination of V260 plus Days 1-15 post-vaccination of IPV in the staggered-use group, across all dose periods and by dose period	X

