Any Vaccine-related Injection-Site AEs	Days 1-15 post-vaccination of V260 and IPV in the concomitant-use group, and Days 1-15 post-vaccination of IPV in the staggered-use group, across all dose periods and by dose period	X
Any Vaccine-related Systemic AEs	Days 1-30 post-vaccination of V260 and IPV in the concomitant-use group, and Days 1-15 post-vaccination of V260 plus Days 1-15 post-vaccination of IPV in the staggered-use group, across all dose periods and by dose period	X
Discontinuation due to any AE	Entire Study Period by Vaccination Group	X
Any Serious AEs including Intussusception	Entire Study Period by Vaccination Group	X

X = results will be provided.

To assess the severity of adverse events, both Sponsor's criteria (see "Assessment of Intensity/Toxicity" in Section 10.3 - Appendix 3) and China Regulatory Agency's criteria (see Section 10.7 - Appendix 7: Country-specific Requirements) will be applied. The incidence of greatest adverse event severity reported by a participant based on both the two criteria will be tabulated for: all injection-site AEs and all systemic AEs across all dose periods.

For the across dose-period summaries and analyses, if the same AE occurs multiple times across dose periods, the AE will be counted once. In order to evaluate any additive safety issues for the concomitant use of V260 and IPV compared to the staggered use of these vaccines, the following summaries will also be provided: Frequencies and percentages of the solicited systemic AEs during Days 1 to 7 after V260 concomitant with IPV in the concomitant-use group, during Days 1 to 7 after V260 alone in the staggered-use group, and during Days 1 to 7 after IPV alone in the staggered-use group.

Any injection-site AEs and vaccine-related injection-site AEs during Days 1 to 30 post-vaccination of V260 and IPV in the concomitant-use group will be summarized separately.

Any reportable safety events collected between Visit 1 and 2 in the concomitant-use group will be listed separately.

For serious adverse events observed during the study, including intussusception, a detailed description will be included in the CSR.

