9.9 Sample Size and Power Calculations

9.9.1 Sample Size and Power for immunogenicity Analyses

This study will randomize 200 participants into the concomitant-use group and 200 into the staggered-use group and has approximately an overall 90.0% power to establish that the concomitant-use group is non-inferior to the staggered-use group in the seroconversion percentage to IPV at 1 month post dose 3 at an overall one-sided, 2.5% alpha-level, if the underlying treatment difference is 0 percentage points. The power and sample size are based on the following assumptions:

1. There is no difference in the true seroconversion percentages for each poliovirus type at 1 month post dose 3 between the concomitant-use and staggered-use groups.
2. The true seroconversion rate for poliovirus types 1, 2, and 3 at 1 month post dose 3 of IPV is 96%, 93% and 97% respectively based on China local IPV studies.
3. The statistical criterion for non-inferiority requires that the lower bound of two-sided 95.0% confidence interval for the difference (concomitant-use group minus staggered-use group) in seroconversion percentages be greater than -10% for each poliovirus type.
4. An 85% evaluability rate for primary immunogenicity analysis population.

Table 6 Sample Size and Power Calculated Based on Neutralizing Antibody Seroconversion Percentage Difference

Antigen	Seroconversion Percentages in Staggered-use Group	Enrolled Participants in Each Group	Effective Sample Size	Power
Poliovirus Type 1	96%	200	170	0.9842
Poliovirus Type 2	93%	200	170	0.9188
Poliovirus Type 3	97%	200	170	0.9953
Overall Power	0.900 [†]			

[†]Overall power is calculated by multiplying the power for each poliovirus type.

The calculation is based on the method proposed by Miettinen and Nurminen [Miettinen, O. and Nurminen, M. 1985] with 170 participants in both groups expected to be included in the analysis and is carried out using PASS 2008. The minimum criterion for success is that the lower bound of two-sided 95% CI of difference >-10%. Given the assumed seroconversion percentage of 95% in the staggered-use group, this may occur when the observed difference in response rates is approximately -3% or larger.

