9.9.2 Sample Size and Power for Safety Analyses

The probability of observing at least one SAE in this study depends on the number of participants vaccinated and the underlying percentage of participants with a SAE in the study population. If the underlying incidence of a SAE is 1.7% (1 of every 59 participants receiving the vaccine), there is a 96.8% chance of observing at least one SAE among 200 participants both in the concomitant-use group and in the staggered-use group. If no SAEs are observed among the 200 participants in any group, this study will provide 97.5% confidence that the underlying percentage of participants with SAE is <1.8% (one in every 67 participants) in the group.

The estimate of and the upper bound of the 95% confidence interval for the underlying percentage of participants with a SAE given various hypothetical observed number of participants with a SAE within the group are provided in Table 7. These calculations are based on the exact binomial method proposed by Clopper and Pearson (1934) [Clopper, C. J. 1934].

Table 7 Estimate of Incidence of SAE and 95% Upper Confidence Bound Based on Hypothetical Number of Participants with SAE Among 200 Participants in the Group

Hypothetical Number of Participants With SAE	Estimate of Incidence	95% Upper Confidence Bound [†]
1	0.5%	2.75%
5	2.5%	5.74%
10	5%	9.00%
20	10%	15.02%
40	20%	26.22%

[†] Based on the two-tailed exact confidence interval of a binomial proportion (Clopper and Pearson, 1934).

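### The safety tables carry no intervals and no between-group contrast, so they do not show how precisely concomitant and staggered use are compared

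*Combined protocol and SAP*

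**What the plan says.** Section 9.6.2 states: "Summary statistics, counts and percentage without confidence interval, will be provided by group". Table 5 marks every safety endpoint for descriptive statistics only, and the summary in Section 9.1 agrees: "All safety data will be summarized as frequencies and percentages for the two vaccination groups". No difference between groups is planned for any safety endpoint.

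Four other places bear on this:

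- Section 9.6.2 gives one set of summaries a comparative purpose: "In order to evaluate any additive safety issues for the concomitant use of V260 and IPV compared to the staggered use of these vaccines". What follows is frequencies and percentages of solicited systemic events in the 7 days after V260 with IPV, after V260 alone and after IPV alone.
- Section 9.6 opens with: "Statistical testing and inference for immunogenicity and safety analyses are described in Section 9.6.1 and Section 9.6.2, respectively". Section 9.6.2 contains neither a test nor an interval.
- Section 9.9.2 rests the safety sample size on a detection probability and on Clopper-Pearson bounds (Table 7). For a group with no SAE it says that "this study will provide 97.5% confidence that the underlying percentage of participants with SAE is <1.8" (in per cent).
- Section 9.6.1 and Table 3 give within-group Clopper-Pearson 95% intervals to the secondary proportions with titers of at least 1:8 and 1:64, although no hypothesis attaches to them.

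**The concern.** Safety is a secondary objective, and one stated purpose of the summaries is to see whether giving the two vaccines together adds to the events seen when they are given apart. That is a comparison. Two bare percentages from groups of about 200 do not tell the reader whether a small gap means little difference or too few infants to see one. If the percentages come out close, the natural reading is that co-administration adds no reactogenicity, even where an increase of several points has not been excluded.

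The descriptive character of the safety analysis does not explain the omission. The plan already attaches intervals to descriptive immunogenicity proportions of the same objective rank, and it uses exact bounds to argue that 200 per group is informative about SAEs. It gives no reason for treating the safety tables differently.

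**Working it through.** **Inputs.** Group size, from Section 9.9.1: "This study will randomize 200 participants into the concomitant-use group and 200 into the staggered-use group". SAE incidence, from Section 9.9.2: "If the underlying incidence of a SAE is 1.7% (1 of every 59 participants receiving the vaccine"). Interval methods: Clopper-Pearson and Miettinen-Nurminen, both already in Section 9.6.1. Event rates for solicited events: not in the documents, so a range of 5% to 30% is assumed.

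**1. The plan's own figures.**

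- Chance of at least one SAE in 200: 1 − (1 − 0.017)^200 = 0.9676. The plan says 96.8%, which agrees.
- Table 7, upper limit = 0.975 quantile of Beta(x + 1, 200 − x). For x = 1, 5, 10, 20 and 40 this gives 2.75%, 5.74%, 9.00%, 15.02% and 26.22%. All five agree.
- No SAE in 200, at 97.5%: 1 − 0.025^(1/200) = 1.83%, or about 1 in 55. This matches the plan's 1.8% after rounding. The plan's parenthesis of 1 in 67 does not match it: 1/67 = 1.49%, which is the one-sided 95% bound, 1 − 0.05^(1/200) = 1.49%. The sentence mixes two confidence levels.

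**2. Precision of the comparison.** The Miettinen-Nurminen limits are the values d at which (p̂₁ − p̂₂ − d) / √V(d) = ±1.96. Here V(d) = [p̃₁(1 − p̃₁)/200 + p̃₂(1 − p̃₂)/200] × 400/399, and p̃₁, p̃₂ are the maximum-likelihood proportions under p₁ − p₂ = d. The simple approximation 1.96 × √[2p(1 − p)/200] is shown as a check.

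| Observed in each group | Miettinen-Nurminen 95% interval | Simple check |
|---|---|---|
| 10/200 (5%) | ±4.6 points | ±4.3 |
| 20/200 (10%) | ±6.1 points | ±5.9 |
| 40/200 (20%) | ±7.9 points | ±7.8 |
| 60/200 (30%) | ±9.0 points | ±9.0 |

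For unequal rates, 50/200 against 40/200 (25% and 20%) gives a difference of 5.0 points with an interval of −3.2 to +13.2.

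**3. Where a difference can be read.** From Section 9.4.2 and Table 5:

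| Endpoint | Concomitant, per dose period | Staggered, per dose period | Match |
|---|---|---|---|
| Solicited injection-site | Days 1–7 after IPV (given with V260) | Days 1–7 after IPV | Yes |
| Any injection-site | Days 1–15 after IPV (given with V260) | Days 1–15 after IPV | Yes |
| SAE | Entire study | Entire study | Yes |
| Solicited systemic, maximum temperature | One 7-day window | Two 7-day windows | No |
| Any systemic | One 30-day window | Two 15-day windows | No |

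Over three dose periods the fourth row means 3 × 7 = 21 days against 6 × 7 = 42 days. Assume a 5% background risk in each 7-day window, independent windows and no vaccine effect at all. The expected proportions with an event are then 1 − 0.95³ = 14.3% and 1 − 0.95⁶ = 26.5%. With 29/200 against 53/200, the Miettinen-Nurminen interval for concomitant minus staggered is −19.9 to −4.1 points. It excludes zero, in favour of concomitant use, from unequal observation time alone.

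**The case against.** The best defence is that the safety plan is deliberately descriptive and consistent: Section 9.1, Section 9.6.2 and Table 5 agree, and no safety hypothesis, margin or success criterion exists. That stands, and it limits the point to reporting.

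A reader might infer that, without intervals, the secondary safety objective and the confidence statement in Section 9.9.2 cannot be delivered at all. The documents do not support this. Section 3 words the objective as an evaluation resting on the proportions of infants with events, and the planned tables give those proportions. Section 9.9.2 is a planning statement about a single group, conditional on hypothetical counts. It does not promise an interval in the results, its bounds follow from the count and the group size that the tables will show, and a between-group difference plays no part in it. SAEs will also be described in detail in the study report.

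It is also fair to say that the summaries after V260 with IPV, after V260 alone and after IPV alone are a sensible display with 7-day windows throughout. They still carry no measure of uncertainty.

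A further objection is that difference intervals on every endpoint would do harm. For the across-period systemic and temperature summaries this is right, as step 3 of the working shows. Bare percentages have the same imbalance, but an interval would present it as a precise treatment effect. The remedy therefore has to be confined to matched windows.

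Finally, how readers will interpret close percentages is a prediction. That is conceded; the width of the intervals does not depend on it.

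**Conclusion.** The point holds as a reporting gap that should be closed. The plan gives part of its safety analysis a comparative purpose and argues from exact bounds when choosing the sample size, then excludes intervals from the tables and plans no contrast. At 200 per group, equal observed percentages leave differences of about 4.6 to 9.0 points possible in either direction as the observed rate runs from 5% to 30%. Those widths assume all 200 infants per group contribute, and they rest on assumed event rates. The objective remains achievable as worded, and neither the primary hypothesis nor the sample size is affected.

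**What to change.** In Section 9.6.2 and Table 5, replace the exclusion of confidence intervals with the following:

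1. Within-group Clopper-Pearson 95% intervals for solicited injection-site events, SAEs, and the three 7-day solicited systemic summaries (after V260 with IPV, after V260 alone, after IPV alone).
2. Concomitant-minus-staggered differences with Miettinen-Nurminen 95% intervals, without tests, for solicited injection-site events (Days 1–7 after IPV), any injection-site events (Days 1–15) and SAEs (entire study). For SAEs, state whether events between Visits 1 and 2 in the concomitant group, which Section 9.6.2 lists separately, are counted, so that the periods do match.
3. No difference interval for the across-period solicited systemic, temperature or any-systemic summaries, with a note that the windows differ between groups.
4. A sentence that all these intervals are descriptive and unadjusted.

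In the same edit, bring the zero-event sentence in Section 9.9.2 to one confidence level, and make the opening of Section 9.6 agree with what Section 9.6.2 contains.

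The cost is a few sentences and some table programming with methods already in the plan. No data collection changes. The remaining downside is that unadjusted intervals may be over-read as tests, which the descriptive label is there to limit.

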9.6.3 Demographic and Baseline Characteristics

The comparability of the groups for each relevant demographic and baseline characteristic will be assessed by the use of summary tables. No statistical hypothesis tests will be performed on these characteristics. The number and percentage of participants screened and randomized and the primary reasons for screening failure and discontinuation will be displayed. Demographic variables (e.g., age, race, gender, birth weight [kg]), medical history, prior and concomitant vaccinations and therapies will be summarized by group either by descriptive statistics or categorical tables.

9.7 Interim Analyses

No interim analyses are planned for this study.

9.8 Multiplicity

There will be no multiplicity adjustment. The success of the study requires demonstrating non-inferiority for all 3 of the poliovirus types described in the primary study hypothesis.

9.9 Sample Size and Power Calculations

9.9.1 Sample Size and Power for immunogenicity Analyses

This study will randomize 200 participants into the concomitant-use group and 200 into the staggered-use group and has approximately an overall 90.0% power to establish that the concomitant-use group is non-inferior to the staggered-use group in the seroconversion percentage to IPV at 1 month post dose 3 at an overall one-sided, 2.5% alpha-level, if the underlying treatment difference is 0 percentage points. The power and sample size are based on the following assumptions:

1. There is no difference in the true seroconversion percentages for each poliovirus type at 1 month post dose 3 between the concomitant-use and staggered-use groups.
2. The true seroconversion rate for poliovirus types 1, 2, and 3 at 1 month post dose 3 of IPV is 96%, 93% and 97% respectively based on China local IPV studies.
3. The statistical criterion for non-inferiority requires that the lower bound of two-sided 95.0% confidence interval for the difference (concomitant-use group minus staggered-use group) in seroconversion percentages be greater than -10% for each poliovirus type.
4. An 85% evaluability rate for primary immunogenicity analysis population.

Table 6 Sample Size and Power Calculated Based on Neutralizing Antibody Seroconversion Percentage Difference

Antigen	Seroconversion Percentages in Staggered-use Group	Enrolled Participants in Each Group	Effective Sample Size	Power
Poliovirus Type 1	96%	200	170	0.9842
Poliovirus Type 2	93%	200	170	0.9188
Poliovirus Type 3	97%	200	170	0.9953
Overall Power	0.900 [†]			

[†]Overall power is calculated by multiplying the power for each poliovirus type.

The calculation is based on the method proposed by Miettinen and Nurminen [Miettinen, O. and Nurminen, M. 1985] with 170 participants in both groups expected to be included in the analysis and is carried out using PASS 2008. The minimum criterion for success is that the lower bound of two-sided 95% CI of difference >-10%. Given the assumed seroconversion percentage of 95% in the staggered-use group, this may occur when the observed difference in response rates is approximately -3% or larger.

